## Improving Southeast Florida's Transit Ecosystem for Students

Version 1.3 June 22, 2021

- 1. Project Summary (3 sentences or less): Florida Atlantic University (FAU) will lead a collaboration with two area colleges and three transit agencies to plan, launch, and evaluate transportation solutions for 6,000 students in Fort Lauderdale, Boca Raton, and Davie. Local students who use transit often face lengthy travel and wait times due to inadequate bus and train schedules, while many more students who buy vehicles spend their limited incomes on car payments, gas, insurance and vehicle maintenance in a highly congested region. Of the 140,000 students at the three participating institutions, more than 40% received Pell grants, and more than 50% are students of color.
- 2. Objectives: The overall goal of the project is to evaluate a program to help students from disadvantaged backgrounds achieve success in college. The Kresge Foundation has identified transportation-related issues as one of the barriers facing minority and first-generation students that make it more difficult for students to attain their educational goals. By opening up a broader range of more affordable transportation options to south Florida campuses, this project endeavors to facilitate information on transportation alternatives, thus mobilizing more resources toward attaining academic goals. As a corollary objective, the researchers will conduct research on a recruitment method (see Student Ambassador Sub-Study).

The Cluster Randomized Controlled Trial (cRCT) portion of the study will focus on evaluating the use of information, marketing, and incentives to shape student travel behavior to campus through the three channels identified in Ajzen's (1991) framework (Error: Reference source not found).

We will evaluate whether a package of information, marketing, and incentives shifts student travel behavior to campus over one year, and in turn if these shifts in travel behavior result in improved academic performance.

Specific objectives of the cRCT include evaluating whether the intervention results in relatively:

- 1. Greater utilization of travel modes alternative to single-occupant vehicle travel (transit, biking, walking, bike-sharing, electric scooters, and carpooling)
- Lower rates of car ownership
- 3. Superior college performance (higher GPAs)
- 4. More credit hours completed
- 5. Higher retention rates

PLEASE SEE: RCT Evaluation Protocol for full details.

3. Introduction, Background, and Significance

[figure not shown]
# Use of Information and Marketing to Influence Travel Behavior

Information, marketing, and incentives have been used effectively to promote transportation alternatives (i.e. travel modes other than driving alone), especially in college campus settings (Ralph & Brown, 2019; Rodriguez & Rogers, 2014; Rose, 2008). This approach is grounded in the Theory of Planned Behavior proposed by Ajzen (1991). Azjen argued that behavior is grounded in intention, and

1588924-5				
Approved On 1	July 22, 2021			
Expires On:	Not Applicable			

that intention, in turn, is influenced by three considerations: 1) A person's attitude towards the behavior, 2) their subjective norm, and 3) their perceived behavioral control.

A person's attitude towards a behavior includes all of the positive and negative outcomes they consider likely to result from the behavior. For example, if a person believes they will be healthier if they bike to work, then they have at least in part a positive attitude towards that behavior. A person's subjective norm concerns how they think others in their social circle evaluate such behavior, whether it is looked on as favorable or unfavorable. If driving or car ownership is considered a

marker of status among students, then such students will be more likely to select driving as the preferred mode. A person's perceived

behavioral control is a person's belief in their ability to put the behavior into action. For example, a student may want to take transit to get to campus but is unfamiliar with the way the local transit system operates. Having an app that can explain information such as board locations,

schedules, and fares may increase the student's sense of perceived behavioral control with respect to taking public transit. Information, marketing, and incentives each can influence each of these considerations, creating the conditions for possible behavior change. Each of these considerations influences the formation of a person's behavioral intention (See Figure 1: Azjen's (1991) Theory of Planned Behavior). Behavioral intention, in turn, is the prelude to behavior or behavior change.

PLEASE SEE: RCT Evaluation Protocol for full details.

The *Improving South Florida's Transit Ecosystem for Students* builds on previous studies that have demonstrated the power of information, marketing, and incentives to shape student travel behavior to campus. One unique element in our study is the focus on the Mobiity-as-a-Service (MaaS) app as a means of providing continuous information and marketing to shape student travel behavior.

#### 4. Research Plan

# (a) Research Design

This study is designed as an unblinded cluster randomized controlled trial (cRCT) in which a cluster of students who live in a particular residence off-campus will be randomly assigned to either the MaaS app or no app; students in a cluster assigned to the MaaS group will also receive information concerning housing options. Cluster randomization will be stratified by campus and whether the student is full or part-time; these stratification factors were chosen because of their influence on student travel modes and school performance. Cluster randomization will use a 1:1 ratio.

The trial will be conducted over one year. A pilot study of 200 students will test the randomization process on the responses from the Informed Consent survey. The pilot will be used to determine a likely response rate to the survey and to identify issues with the survey rollout. PLEASE SEE: RCT Evaluation Protocol for full details.

I	1588924-5		
	Approved On	July 22, 2021	
ĺ	Expires On:	Not Applicable	

# (b) Research Methods

The Mobility-as-a-Service (MaaS) App will be provided to students in the Intervention Group and is intended to facilitate their use of alternative transportation modes such as public transit, ride-hailing, walking, biking, bike share, and e-scooter share to get to campus. The MaaS App will be downloaded to students' smartphones and will provide real-time, multimodal trip planning to students on demand when they open the app. This means, for instance, that a student can plan a trip that includes driving to a train station, taking the train, and then walking from the alighting train station to their final destination. The app will be white label, i.e. it will have a customized look and feel specific to the participating south Florida colleges, and it will have personalization features so that students can tailor the app to their travel patterns.

PLEASE SEE: RCT Evaluation Protocol for full details.

The Cluster Randomized Controlled Trial (cRCT) portion of the study will focus on evaluating the use of information, marketing, and incentives to shape student travel behavior to campus through the three channels identified in Ajzen's framework (Error: Reference source not found).

There will be three sources of quantitative data: 1) student surveys will provide information on student travel behavior; 2) official academic records will provide data on student academic performance; and 3) student app usage will be derived directly from the app.

Student travel behavior for both intervention and control populations will be collected through regular surveys conducted at baseline and each of the two semesters (See Appendix 4 – Student Travel Behavior Survey for the full survey text). We will issue a baseline travel behavior survey at the beginning of the project and then issue regular surveys during fall and spring semesters for the one-year observation period.

We will also ask questions regarding the students' demographics, a few questions about attitudes towards alternative modes and self-reported BMI and health related quality of life, and a few questions concerning their suggestions for potential improvements for travel to campus.

These data will be complemented with academic performance and achievement data derived from official university/college administrative records. Student academic performance data will include grade point average for each semester, credit hours completed for each semester, and related academic outcomes, i.e. degree attainment, persistence in their program, and/or dropping out of their program. We will track the performance of students who transfer out of one of the three colleges via the National Student Clearinghouse Database. Using name and date of birth, we will be able to identify students who leave whether they dropped out or continued in another program. We will also be able to determine if they completed a degree.

# (c) Population

The study population will be students who live off-campus who attend any of the following three colleges or universities: Florida Atlantic University (FAU), Broward College (BC), or Palm Beach State College (PBSC). To qualify for the study, students must plan to be at the same institution for the next year. The sample will be derived from a population of almost 51,000 students living off-campus (see Table1 below). Students will be enrolled currently at one of four campuses: The Book Patent Campus-

Institutional Review Board

Expires On: Not Applicable

the main campus for Florida Atlantic University (FAU) and a satellite campus for Palm Beach State College (PBSC); the Fort Lauderdale campus—a satellite campus for Florida Atlantic University and Broward College (BC); the Davie campus—the main campus for Broward College and a satellite campus for Florida Atlantic University; and the Lake Worth campus, the main campus for Palm Beach State College. The distribution of full-time and part-time off-campus students for each college and campus are provided in Table 1 below.

College	FAU	PBSC	FAU	ВС	FAU	ВС	PBSC	
Campus	Boca	Boca	Fort	Fort	Davie	Davie	Lake	Total
	Raton	Raton	Lauderdale	Lauderdale			Worth	
Enrollment								
Status								
Part-Time	9,417	3,734	100	330	1,613	5,990	8,273	29,457
Full-Time	13,115	1,537	109	114	1,713	3,608	3,108	23,304
Total	20,647	5,271	245	444	3,326	9,598	11,381	50,912

# (d) Recruitment

We will recruit students primarily through an email sent by each campus' administration. However, we will engage in a concerted marketing campaign to recruit students to participate in the study. Also, the study will have a website and a social media page through which students can self-enroll. Students will be made aware of the study for several months before the enrollment email, by integrated web banners into administrative emails including banners on the parking page and administrative webpages such as Canvas. We will also produce flyers and posters and place them in prominent locations around each campus. Each 'email contact' will be a series of four emails: a heads-up email, two "action now" emails, and one follow-up email as a reminder or thank you. For more information on the student engagement strategy, see Appendix 2 – Promoting Participation in the Study to College Students.

In addition, we will employ "Student Ambassadors," up to 10 students who will attend events and other places students gather on campus. The Ambassadors will not administer the survey—they will promote it. Ambassadors will not collect consent forms or data. The Ambassadors will receive a training beforehand about appropriate recruiting behaviors.

# Ambassador Sub-Study

The inclusion of Student Ambassadors represents an additional strategy to recruit participants for the main research study (see above). In the Ambassador sub-study, conducted at the end of the main study recruitment phase, the research team seeks to understand what worked well and what obstacles the Student Ambassadors encountered. The sub-study contributes to generalizable knowledge about recruitment.

Research Design: A qualitative analysis of answers to open-ended questions will be carried out by members of the main research team under the direction of the principal investigator. In this

1588924-5			
Approved On:	July 22, 2021		
Expires On:	Not Applicable		

way, the Ambassadors will serve as additional research participants, and this research is ancillary to the main research study's focus. See attached Focus Group protocol.

Research Method: The research team will convene a one-hour debriefing focus group with the Ambassadors to ask about successful strategies and barriers to recruiting students. A separate consent form for Ambassadors is attached. We will ask focus group participants to refrain from mentioning any names (themselves or others) during the session. The participants will remain anonymous during the data collection, analysis, and in any resultant research papers. We do not foresee any risks to participants. Participants will be compensated for their time.

Population: A maximum of 10 Ambassadors will participate, 18 years of age or older.

Recruitment: This session will be optional for Ambassadors, and only open to Ambassadors. Ambassadors will receive a consent form. If they would like to participate, they will be asked to complete the form and submit it.

Analysis: Focus group transcripts will be analyzed to identify successful strategies and obstacles to success.

# (e) Analysis Plan

From the data collected above in (b) **Research Methods**, we will derive the following major outcome variables, relevant to each of the major research questions:

- 1. Will students in the intervention group, subject to information, marketing incentives as delivered through a MaaS app, be more likely to use alternative modes to reach campus?
  - a. Students who always take alternative modes to campus
  - b. Students who sometimes take alternative modes to campus
  - c. Students who always take an automobile to campus
- 2. Will students in the intervention group, subject to information, marketing incentives as delivered through a MaaS app, reduce their level of car reliance?
  - a. Student car ownership
  - b. Single-occupant vehicle travel
- 3. Will students who make more frequent use of alternative modes to campus and/or reduce car ownership have improved school performance?
  - a. Grade point average
  - b. Credit hours earned
  - c. Retention, degree completion, drop out status, and/or transfer status, as relevant

TATI	1588924-5		
	Approved On	July 22, 2021	
Institutional Review Board	Expires On:	Not Applicable	

Bivariate analyses will be conducted between each ordinal outcome (i.e. changes in transportation: from less green to green, or green to less green; grades) and demographic and commuting characteristics at baseline using logistic or ordinal logistic regression. Bivariate analyses between longer scale continuous variables (i.e. numeric grade point average) and demographic and commuting characteristics will be determined using linear regression. Associations between continuous outcomes and continuous covariates will be assessed using Pearson or Spearman Rank correlations. Covariates for which bivariate analyses result in p-values less than .20 for baseline and other covariates will be included in an initial mixed-effects (hierarchical) models along with variables and interactions that have been specified by content experts a priori. A monitored step-wise procedure will be used to eliminate covariates from the initial model: that variable with the highest non-significant p-value (p>.05) will be eliminated (provided it is not part of an interaction effect). The final model will include significant variables as well as those determined a priori to control in every model (i.e. distance from residence to public transportation). Models with different covariance structures will be assessed, and that with the lowest Akaike Information Criterion will be chosen. Should these models not converge, generalized estimating equations will be used.

PLEASE SEE: RCT Evaluation Protocol for full details.

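### The academic objectives are worded as effects of the intervention, but the analysis questions attach GPA, credit hours and retention only to a comparison by travel behaviour observed after randomisation

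*Protocol*

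**What the plan says.** Protocol section 2 introduces its numbered list with "Specific objectives of the cRCT include evaluating whether the intervention results in relatively". Items 1 and 2 concern alternative modes and car ownership. Item 3 is higher GPA, item 4 is "More credit hours completed" and item 5 is "Higher retention rates". The paragraph before the list states a further aim: whether the package shifts travel behaviour "and in turn if these shifts in travel behavior result in improved academic performance".

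Section 4(e) then ties outcomes to three research questions. Questions 1 and 2 ask about students in the intervention group; their outcomes are mode use, car ownership and driving alone. Question 3 reads "Will students who make more frequent use of alternative modes to campus and/or reduce car ownership have improved school performance" and carries GPA, credit hours and retention, with degree completion, drop-out and transfer. It does not mention the intervention group.

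Travel behaviour comes from "regular surveys conducted at baseline and each of the two semesters" (section 4(b)). The Dissemination text plans a paper on the academic performance impacts of the app and its accompanying marketing and information.

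**The concern.** Objectives 3 to 5 ask a causal question that randomisation can answer: does assigning a residence to the intervention improve its students' academic results? Question 3 asks something else: do students who travel differently, or who give up a car, do better? The grouping in question 3 arises after assignment and is itself the outcome of questions 1 and 2, so randomisation does not balance the groups being compared.

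The protocol itself recognises common causes of travel and grades. Section 4(a) says "Cluster randomization will be stratified by campus and whether the student is full or part-time" and gives as the reason that these factors influence both travel modes and school performance.

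If the academic conclusion were drawn from question 3, a positive result would show that students with different travel habits have different grades. It would not show that offering the app improved grades. The two contrasts can disagree: question 3 may be clearly positive while the arms hardly differ.

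**Working it through.** **Step 1. Map objectives to questions.** The protocol gives no effect size or power figure on this point, so there is nothing to reproduce. The check is a side-by-side reading of sections 2 and 4(e).

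| Objective (section 2) | Question (section 4(e)) | Groups compared |
|---|---|---|
| 1. Alternative modes | 1 | Intervention group named |
| 2. Car ownership | 2 | Intervention group named |
| 3. GPA | 3 only | Travel behaviour or car ownership |
| 4. Credit hours | 3 only | Travel behaviour or car ownership |
| 5. Retention | 3 only | Travel behaviour or car ownership |

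Two of three questions name the intervention group, and neither carries an academic outcome. Three of five objectives therefore have no by-arm question in this document.

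**Step 2. Does the modelling text close the gap?** It does not. The second part of section 4(e) describes bivariate screening, mixed models and stepwise elimination without naming arm as a term for any outcome, travel outcomes included. It admits variables specified a priori, and arm could be one of them. It neither repairs question 3 nor shows that arm is left out for the academic outcomes in particular.

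**Step 3. Are the two contrasts the same quantity? (Illustration on assumed values.)** Suppose there is no confounding and the intervention affects GPA only through travel. Let d be the share of students whom the intervention shifts to alternative modes, and b the GPA effect of being shifted. Then

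arm effect = d × b.

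With b = 0.20 SD:
- d = 0.05: 0.05 × 0.20 = 0.01 SD
- d = 0.10: 0.10 × 0.20 = 0.02 SD
- d = 0.20: 0.20 × 0.20 = 0.04 SD

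The question 3 figure is 1/d = 20, 10 or 5 times the arm effect. This is a difference between two estimands, not a bias.

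**Step 4. What could a by-arm comparison detect?** With 80% power, a two-sided 5% test and 1:1 allocation,

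detectable difference = 2.80 × (2/√N) × √DE, where DE = 1 + (E[m²]/E[m] − 1) × ICC.

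Assume that residences hold one or two students with equal chance. Then E[m²]/E[m] = 2.5/1.5 = 1.67 and DE = 1 + 0.67 × ICC.

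| N (assumed) | ICC 0 | ICC 0.05 | ICC 0.20 |
|---|---|---|---|
| 6,000 | 0.072 SD | 0.074 SD | 0.077 SD |
| 3,000 | 0.102 SD | 0.104 SD | 0.109 SD |

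For example, 2.80 × 2/√6,000 = 5.60/77.46 = 0.072. The 6,000 is the project figure in section 1, not a stated analysis number. On these values the arm effects in step 3 (0.01 to 0.04 SD) lie below what could be detected, so the correct contrast might well be null.

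**The case against.** **Deferral to another document.** Section 4(e) is an outline, and the protocol repeatedly refers to an RCT Evaluation Protocol for full details. A reader might infer from question 3 that the trial has no randomised analysis of academic outcomes. The document does not support that, because the by-arm analysis may be in the text not shown. What stands is narrower: section 4(e) does attach a contrast to the academic outcomes, and it is not the one in objectives 3 to 5. This is a mismatch between two statements, not silence.

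**Question 3 has a purpose.** It matches the mechanism aim in section 2, so it would be wrong to call it an error in itself. That aim is separate from the numbered objectives, and meeting it does not answer them. The Dissemination text does not say which analysis the academic paper will use, so one cannot say that the paper will rest on question 3, only that question 3 alone could not support it.

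**Size of any confounding.** A reader might infer that question 3 will often be falsely positive. That depends on how it is read. If students are compared by their level of mode use at follow-up, an unmeasured factor that drives both travel and grades biases the result, and adjusting for baseline GPA need not remove it. If they are compared by change from baseline, as the references to reduced car ownership and to changes in transportation allow, a stable factor with constant influence cancels: with M0 = rU + e0 and M1 = rU + e1, M1 − M0 = e1 − e0, which is free of U. Factors that change during the year, such as working hours, could still bias a change comparison. The documents do not settle the reading, so no false-positive rate is claimed here.

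**Low power of the arm comparison.** On the illustrative values it would usually be null. That is a reason for modest expectations, not for letting a different contrast stand in for the randomised one.

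**Conclusion.** The point holds as a mismatch within this document. Objectives 3 to 5 name an intervention effect, while section 4(e) gives those outcomes only a comparison by behaviour observed after randomisation. Its size is 3 of 5 objectives without a by-arm question, and this count rests on the text alone. That question 3 does not estimate the intervention effect follows from its wording and from the timing of the follow-up surveys, and needs no numerical assumption.

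The figures in steps 3 and 4 are illustrative. They assume travel as the sole path, and d, b, ICC, residence size and N are all assumed. They show only that the two contrasts can differ several-fold, and that a by-arm effect may be smaller than the roughly 0.07 to 0.10 SD detectable with 6,000 or 3,000 students. The mismatch should be fixed. It does not show that the randomised academic analysis is missing from the trial.

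**What to change.** Add a question to section 4(e) along these lines: *Do students in residences randomised to the intervention have higher GPA, more credit hours completed and higher retention than students in residences randomised to control?* State that it is analysed by assigned arm with residence clustering accounted for, that arm stays in the model whatever the covariate screening and stepwise elimination remove, and that post-randomisation travel behaviour is left out of this model.

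Label question 3 a secondary, observational analysis of the mechanism aim, and say whether it uses the level of travel behaviour or its change from baseline. Base any statement on the app's academic impact, including the planned paper, on the arm comparison. If the RCT Evaluation Protocol already contains the by-arm analysis, state that contrast in section 4(e) so that the two documents agree.

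The cost is one question and a few sentences. No new data are needed: section 4(b) already plans semester GPA, credit hours and persistence from official records. The arm indicator is held in the Student Communications Data Set and can be linked by study ID, which the by-arm travel questions require in any case.

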### 7. Informed Consent Process:

- (a) Each college will invite students who meet the following exclusion criteria to participate in the study:
  - Enrolled as of September 1, 2020
  - The student lives off-campus
  - The student is enrolled at FAU, Broward College or Palm Beach State College and is affiliated with either the Boca Raton, Fort Lauderdale, Davie or Lake Worth campus

The invitation to participate in the study will ask the student to provide informed consent, and will ask four exclusion questions:

- Do you live off-campus?
- If student lives off campus, what is their address?
- Do you own a smartphone?
- What is your smartphone number? (for study communication purposes)
- Do you expect to be at [the same institution] until December 2022?

If the student answers 'yes' to the above questions, provides their phone number, address of residence and informed consent, then they will be enrolled in the cRCT and randomized when enrollment is complete.

The flow of students to be enrolled in the study is presented in Figure 2: Sample Flow Diagram below.

1588924-5		
Approved On-	July 22, 2021	
Expires On:	Not Applicable	

[figure not shown]

Figure 2: Sample Flow Diagram

- (b) No deception will be used.
- (c) We do not plan to enroll cognitively- or decisionally- impaired subjects.
- (d) We do not plan to enroll prospective subjects as emancipated minors.
- (e) We do not plan to recruit non-English speaking subjects.
- 8. Informed consent will be online.
- 9. Research Materials, Records, and Privacy:

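### Models for record-based academic outcomes draw on survey-based commuting covariates, so randomised students with known outcomes can drop out of the arm comparison

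*Protocol*

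**What the plan says.** **Outcomes.** Section 4(b), Research Methods, takes "academic performance and achievement data derived from official university/college administrative records". It continues: "Student academic performance data will include grade point average for each semester, credit hours completed for each semester, and related academic outcomes". Leavers are followed without a survey: "We will track the performance of students who transfer out of one of the three colleges via the National Student Clearinghouse Database". Section 2, Objectives, makes GPA, credit hours and retention objectives of the randomised intervention.

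**Covariates.** Travel data have another source: "Student travel behavior for both intervention and control populations will be collected through regular surveys conducted at baseline and each of the two semesters". Section 4(b) adds: "We will also ask questions regarding the students' demographics". Section 4(f) offers participants no compensation.

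**Entry to the trial.** Under section 7, a student who passes the screening questions and "provides their phone number, address of residence and informed consent, then they will be enrolled in the cRCT and randomized when enrollment is complete". Completing the travel survey is not among the conditions.

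**Model building.** Section 4(e) states: "Bivariate analyses between longer scale continuous variables (i.e. numeric grade point average) and demographic and commuting characteristics will be determined using linear regression". Covariates with a bivariate p-value below .20 then go into the initial mixed model. The entry rule is not limited to baseline covariates. Terms with p > .05 are removed stepwise unless they are part of an interaction or were fixed in advance. The only forced covariate named is distance from residence to public transportation.

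**The concern.** The academic outcomes are the most complete and objective data in an unblinded trial, and they can be analysed in essentially everyone randomised. Section 4(e) links them to covariates that exist only for students who returned a survey. A mixed model fitted by default omits any record with a missing covariate, so one survey variable in the model is enough to remove non-responders whose GPA or status is known.

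The number of students analysed would then depend on survey response, and on which covariates pass the screen for each outcome. GPA, credit hours and retention could be compared on different subsets of the randomised students.

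**Working it through.** **No plan figure to reproduce.** The protocol states no response rate, power, effect size or calculated sample size. The 6,000 students in the Project Summary are a project figure. The check is therefore a tracing of data sources, followed by arithmetic on assumed values.

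**Step 1. Who has which variable?**

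| Variable | Source | Survey needed? |
|---|---|---|
| GPA, credit hours, status | Administrative records; national database for leavers | No |
| Distance to public transportation | Computable from address given at enrolment | No |
| Campus, full/part-time | Stratification factors | No |
| Other commuting characteristics | Travel survey | Yes |
| Demographics | Asked in the survey; some also listed in the Student Performance Data Set, source not stated | Unclear |

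A student can be randomised and have academic outcomes, yet have no commuting data beyond the address.

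**Step 2. How easily does a survey covariate enter?** With k independent commuting variables unrelated to GPA, the chance that at least one passes p < .20 is 1 − 0.8^k. For assumed k = 5 this is 1 − 0.328 = 67%; for k = 10 it is 1 − 0.107 = 89%. This concerns entry to the initial model, not survival to the final one.

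**Step 3. Cost in precision.** Let r be the assumed share of students with the covariate. Treating students as independent, the standard error is multiplied by 1/√r. A comparison with 80% power in everyone (also assumed; two-sided 5%) falls to Φ(2.8016√r − 1.96). Adjustment multiplies the variance by (1 − R²)/r, so the survey covariates break even only if R² = 1 − r.

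| r | SE increase | Power | Break-even R² |
|---|---|---|---|
| 0.9 | 5% | 76% | 10% |
| 0.8 | 12% | 71% | 20% |
| 0.7 | 20% | 65% | 30% |
| 0.6 | 29% | 58% | 40% |

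For scale, take the 6,000 as the trial size with 3,000 per arm. The detectable GPA difference is 2.8016 × √(2/3000) = 0.072 SD. At 70% response (2,100 per arm) it is 0.087 SD.

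**Step 4. Clustering.** With m students per residence, intracluster correlation ρ, and non-response spread within residences that each keep a responder, the variance ratio is (1/r) × (1 − ρ + rmρ)/(1 − ρ + mρ). For ρ > 0 and r < 1 the second factor is below 1, so the loss is smaller than in Step 3.

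**Step 5. Does it bias the arm effect?** This was simulated with 2,000,000 records, standardised GPA, zero true effect, and response rising with GPA (log-odds 0.5 per SD except where shown). All inputs are assumed.

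| Response, control v intervention | Responders-only difference |
|---|---|
| 59% v 59%, same GPA slope | 0.00 SD |
| 59% v 70%, same GPA slope | −0.05 SD |
| 50% v 70%, same GPA slope | −0.09 SD |
| 60% v 59%, GPA slope 0.25 v 0.5 | +0.09 SD |

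The analysis of all students gave 0.00 SD throughout. Bias appears only when response, or its dependence on GPA, differs by arm.

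**The case against.** A reader might infer that the plan turns the academic comparison into a responders-only one and so loses the randomised comparison. The documents do not support that.

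- Section 4(e) nowhere says that students lacking a covariate are dropped. It refers to a separate RCT Evaluation Protocol, and handling of missing covariates may sit there or in an analysis plan that is not shown. Silence on it is no finding.
- Passing p < .20 is not enough. A commuting variable can be removed again at p > .05, so the final GPA model may hold no survey covariate. The one named forced covariate comes from the address.
- If the baseline survey precedes assignment, restriction to its responders keeps the arms comparable. Section 4(b) places that survey only at the beginning of the project, so the order is not fixed. That non-responders are likelier to drop out of college is conjecture.
- The response rates and the 80% starting power are assumptions, and Step 3 ignores clustering.
- Question 3 in section 4(e) relates academic outcomes to mode use and car ownership. These are survey-measured, so that analysis is confined to responders whatever covariates are chosen.

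All of this stands, and it limits the point to a conditional one. What remains is that section 4(e) itself selects survey-based covariates for record-based outcomes, and the screens of those covariates necessarily run on responders. Because the entry rule is not limited to baseline covariates, variables from the semester surveys, collected after unblinded assignment, are not excluded either.

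**Conclusion.** The point holds in conditional form, as an inexpensive improvement. If a survey covariate is in the fitted model and incomplete records are omitted, randomised students with known GPA, credit hours or status leave the comparison by arm.

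For assumed response of 60 to 90%, the standard error grows by about 29 to 5% before clustering, and by somewhat less with positive intracluster correlation. Commuting variables would have to explain 40 to 10% of the variance in GPA to repay this; I assume they explain far less.

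The cost is otherwise one of representativeness. Bias requires response to differ by arm. That is possible if the survey follows unblinded assignment or if semester-survey variables are used as covariates, but the protocol does not show that either will happen.

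**What to change.** Add to the modelling paragraph of section 4(e):

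> The comparison of GPA, credit hours and outcome 3c by randomised arm includes all randomised students. It adjusts only for campus, full- or part-time status, address-based distance to public transportation, and those fields of the Student Performance Data Set that are held for all students as recorded at randomisation. Models adjusted for survey variables, and the travel-exposure analysis of question 3, are secondary. If a survey covariate measured before randomisation is kept in the arm comparison, missing values receive a missing category or the overall mean, so that no student is dropped.

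The limit to fields held for all students matters because the data set list does not say which fields come from records. The filling rule is confined to covariates measured before randomisation, since those cannot be affected by assignment. Question 3 remains available.

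The cost is a short paragraph of text and the small precision that commuting variables might add to the academic models.
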